#### Study population

Patients are eligible if (1) aged < 18 years; (2) admitted to an intensive care unit of a participating hospital; (3) for any (critical illness) necessitating ventilatory support for at least 12 hours. We exclude premature infants, i.e., patients with a postconceptional age corrected for gestational age < 37 weeks.

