#### Main study endpoints

The primary endpoint is a set of key ventilation settings and ventilation parameters, including tidal volume (VT), peak inspiratory pressure (PIP), plateau pressure (Pplat), positive end-expiratory pressure (PEEP), inspired fraction of oxygen (FiO2), inspiration to expiration ratio (I:E), inspiration time, set respiratory rate, total respiratory rate, compliance (Crs), driving pressure ( $\Delta$ P) and the mechanical power of ventilation (MP). Secondary endpoints include the incidence of PARDS, duration of ventilatory support, the number of days free from ventilatory support at day 28, length of ICU stay, and ICU mortality. We will also determine whether there are potentially modifiable factors that have an independent association with outcome.

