#### 4.2. Inclusion criteria

Patients are eligible if:

- aged < 18 years;
- admitted to an intensive care unit (ICU) of a participating hospital during the period of data collection; and
- receiving ventilatory support > 12 hours.

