### 5.2.3. Data collection at day of intubation

(note that this could also be the day of admission to a pediatric ICU if transferred from another hospital with mechanical ventilation)

- Date of ICU admission; and
- Date and time of intubation (if the patient is transferred from another hospital than day 0 is the day of admission).

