### 5.2.5. Follow-up

Outcome data will be collected at ICU discharge:

- PARDS (y/n), according to the 2023 Pediatric Acute Lung Injury Consensus Conference (PALICC) definition (24);
- Air leak during ICU stay;
- Intubated (y/n), and if not, extubation date;
- Successful extubation; defined as no reintubation within 48 hours after extubation (y/n), if not: reason of reintubation;
- Alive (y/n), and if not, date of death in ICU; cause of death;
- Number of ventilation-free days at day 28 (zero in case of death or start ECMO);
- Date of discharge from ICU; and
- Destination after ICU discharge (other ICU, ward or home).

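### Intubation is recorded by date and time but extubation by date only, so the duration of invasive ventilation is known only to within a window of up to 24 hours (minor; cheap to improve)

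*Protocol*

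**What the plan says.** **Start of invasive ventilation.** Protocol 5.2.3 lists "Date and time of intubation". For a child transferred from another hospital, day 0 is the day of admission.

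**End of invasive ventilation.** Protocol 5.2.5 lists "Intubated (y/n), and if not, extubation date". For a child who dies in the ICU it asks for the date of death, again without a time. The daily record in 5.2.4 is one morning observation, up to day 3 at most. It shows that support was running that morning, not when it stopped.

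**Use of the interval.** The Summary (Main study endpoints) states: "Secondary endpoints include the incidence of PARDS, duration of ventilatory support, the number of days free from ventilatory support at day 28". Sections 2.1 and 2.2 name duration as an outcome for the association analyses, although the list in 5.1.3 omits it. Section 7.2 plans Kaplan–Meier curves for liberation from the ventilator.

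**Entry.** Section 4.2 requires "receiving ventilatory support > 12 hours". This refers to ventilatory support of any kind, not to intubation.

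**The concern.** The start of the interval carries a clock time and entry is set in hours, yet the end is kept only to the day. The protocol does not say that duration is counted in calendar days, which is the reading under which a date alone would be deliberate. This is a data-collection field: no analysis plan can recover a time that was never recorded.

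At stake is the precision of one secondary endpoint, mainly for children ventilated for a day or two. Two children with the same 14 hours of ventilation show the problem. One ventilated 07:00 to 21:00 scores 0 days by date difference; one ventilated 19:00 to 09:00 scores 1 day. A further loss is that some short stays cannot be compared with 12 hours from the stored data.

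**Working it through.** The protocol gives no figure for recording precision or for the distribution of durations, so there is no stated result to reproduce. Its only numerical input here is the 12-hour limit (4.2). The rest is interval arithmetic plus labelled assumptions.

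**1. What the stored fields allow.** Let *t* be the clock hour of intubation (0 to 24), *k* the number of calendar dates from intubation to extubation, and *D* the true duration. Then

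max(0, 24k − t) ≤ D < 24(k + 1) − t.

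The window is 24 h wide for k ≥ 1 and narrower for a same-date extubation. Taking the midpoint, the error is at most 12 h and averages 6 h once D is 24 h or more: 6/24 = 25% at 24 h, 6/48 = 12.5% at 48 h, 6/120 = 5% at 120 h. At 14 h, with intubation uniform over the day, simulation gives a mean of about 35%.

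**2. Error of date minus date.** Assume intubation times uniform over 24 h.

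- *Extubation at any hour.* If D exceeds a whole number of days by u hours, the error is 24 − u with probability u/24 and −u otherwise. Its mean is 0 and its variance u(24 − u). Averaged over u from 0 to 24 the variance is 24²/6 = 96, so SD = √96 = 9.8 h.
- *Extubation between 08:00 and 18:00.* The error is intubation hour minus extubation hour. Its mean is 12 − 13 = −1 h, its variance 24²/12 + 10²/12 = 48 + 8.3 = 56.3, and SD = √56.3 = 7.5 h.

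**3. Relative size.** This needs a distribution, which the protocol does not give. Assume log-normal durations, median 2 to 5 days, log-SD 0.9, kept if above 12 h. Simulated over both extubation patterns:

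| Quantity (date minus date) | Range |
|---|---|
| Mean error | 0 to −1 h |
| Error SD | 7.5 to 9.8 h |
| Mean absolute error, D < 48 h | 21% to 32% of D |
| Children with D > 12 h scored as 0 days | 0.2% to 4% |
| Correlation with true duration, all | 0.993 to 0.999 |
| Correlation with true duration, D < 48 h | 0.70 to 0.80 |

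**4. Comparing invasive ventilation with 12 hours.** From the window in step 1:

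- k = 0, intubated after noon: D is below 12 h.
- k = 0, intubated before noon: undecidable.
- k = 1, intubated before noon: D exceeds 12 h.
- k = 1, intubated after noon: undecidable.
- k ≥ 2: D exceeds 12 h.

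For a true D between 12 and 36 h and uniform intubation times, the undecidable share is (36 − D)/24: 22/24 = 92% at 14 h, 18/24 = 75% at 18 h, 12/24 = 50% at 24 h, 6/24 = 25% at 30 h, and none from 36 h.

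**The case against.** The case for leaving the field as it is has real weight.

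- **Day resolution can be defended.** The Summary (Study design) aims to keep data collection minimal, the companion outcome of ventilation-free days is counted in days, and the unit of duration is something an SAP commonly fixes. Date minus date is almost unbiased and ranks children almost correctly overall. This stands, and it is why the point is minor.
- **Other items are not affected in the same way.** Ventilation-free days and reintubation within 48 hours are entered in 5.2.5 as items of their own. This stands.
- **The entry rule is applied elsewhere.** A reader might infer that the 12-hour rule cannot be checked at all. The documents do not support that. Under 5.4 the researcher enrols patients and visits centres to collect data, so the chart can be consulted. The stored fields also settle the 12-hour comparison for every stay of 36 h or more and for some shorter ones. What is lost is later confirmation from the database for some short stays.
- **An extubation time would not by itself decide eligibility.** A child with 8 h of noninvasive support followed by 6 h intubated has 8 + 6 = 14 h of support, yet the intubation–extubation pair gives 6 h. Children never intubated, who enter after the first year (4.4), have neither timestamp. For transferred children day 0 is the day of admission.

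A reader might also infer that every duration is understated by about half a day. That follows only if the extubation date is treated as midnight and the intubation time is subtracted from it. The protocol prescribes no such derivation.

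**Conclusion.** The mismatch between 5.2.3 and 5.2.5 is real, and it limits what can be known about the duration of invasive ventilation to a window of up to 24 h. Under date-minus-date counting the cost is random imprecision rather than bias: an SD of about 7.5 to 9.8 h, negligible against long stays but about 21% to 32% mean absolute error for children ventilated under 48 h. The SDs rest on uniform intubation times and the two extubation patterns; the percentages rest also on the assumed log-normal distribution. The protocol does not give the share of short stays, so the effect on the whole cohort is not established.

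It would go too far to say that for short stays the endpoint mainly reflects the hour of intubation: even below 48 h the correlation with true duration is 0.70 to 0.80. Nor is any systematic bias in the association analyses shown. This is a cheap gain in precision, not a flaw that threatens the study's conclusions.

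**What to change.** In 5.2.5, record extubation by date and time, and add the time of death for children who die while ventilated. Derive the duration of invasive ventilation in hours from these and the intubation time in 5.2.3. For transferred children, say whether duration counts from intubation or from admission.

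Use the timestamp pair as supporting evidence on the 12-hour rule, not as the test of it, since the rule covers noninvasive support as well.

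If the extra field is not wanted, state that duration is counted in calendar days. That makes the resolution explicit but does not recover precision for short stays.

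Cost: one extra field per patient (two for deaths), taken from the same chart entry as the date, in a study that aims to keep data collection minimal. The pilot in 5.4 is a natural place to try it. No sample-size figure changes.

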#### Objective

To a) describe the practice of ventilatory support in critically ill pediatric patients, b) to identify potentially modifiable ventilation setting and parameters that have independent associations with outcome including duration of ventilatory support, the number of days free from ventilatory support at day 28, length of ICU stay, and ICU mortality and c) to study the prevalence of the Pediatric Acute Respiratory Distress Syndrome (PARDS).

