#### 2. OBJECTIVES & HYPOTHESES

#### 2.1. Objectives

The aims of this study are to:

- describe the practice of ventilatory support;
- study temporal changes in practice of ventilatory support;
- study geo–economic differences in ventilatory support and outcomes in critically ill pediatric patients; and
- identify potentially modifiable factors that have independent associations with outcome including duration of ventilatory support, the number of days free from ventilatory support at day 28, length of ICU stay, and ICU mortality.

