### 4.4. Sample size calculation

To investigate the association of a limited set of pre-specified confounders with mortality in critically ill pediatric patients receiving invasive ventilation using logistic regression we estimate to need 100 events using the 10 event per variable of thumb. We aim to add 10 covariates to the model. With a conservative estimate of overall PICU mortality of 3% (1, 23) 3300 patients are needed for this analysis. With a conservative estimate of 50 participating centers, including 30 patients per inclusion period, the first analyses can be performed after the first year of inclusions. To explore differences between age groups (< 1 month, 1-11 months, 1-2 years, 3-6 years, 7-12 years, 13-18 years) and to do the same analysis in these groups we need around 19.800 patients in total. Taking a dropout of participating centers of around 30% into account, we expect to reach this sample size after including patients for eight years. After the first year, we will also start to include patients receiving other types of ventilatory support (i.e., noninvasive ventilation (NIV), high-frequency oscillatory ventilation (HFOV), continuous positive airway pressure (CPAP), bi-level positive airway pressure (BiPAP), and high-flow nasal oxygen (HFNO)). As some of these types, for example HFOV, are less frequently used and to be able to do the same analysis, we expect to need to include patients for approximately 10 years.

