### 5.1.3. Clinical outcomes

The clinical outcomes involve the incidence of Pediatric Acute Respiratory Distress Syndrome (PARDS); number of ventilation-free days at day 28; duration of ICU stay; ICU mortality and cause of death.

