## 5.2.2. Medical status

- Comorbidities (pulmonary, cardiac, neuromuscular, syndrome/genetic abnormalities, oncologic, organ transplant, chronic ventilation, mental retardation);
- Reason of ventilatory support; and
- Pediatric Risk of Mortality (PRISM) or Pediatric Index of Mortality (PIM) score, depending on which scoring system is used in the Pediatric Intensive Care Unit (PICU).

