### 5.2.4. Daily data collection

(this is for the first three full calendar days in the pediatric ICU)

At start of ventilation or at arrival when the patient has been intubated in another hospital, ventilation data will be collected directly and after 1 hour (name 'day 0'). Thereafter, ventilation data will be collected daily at a time point in the morning representing a steady state overnight, e.g., before the first morning blood gas is drawn, up to day 3, or the day of extubation or death.

- Type of ventilatory support: invasive ventilation; noninvasive ventilation (NIV), high–frequency oscillatory ventilation (HFOV), continuous positive airway pressure (CPAP), bi-level positive airway pressure (BiPAP), and high–flow nasal oxygen (HFNO);
- Type of airway management: intubation or tracheostomy (invasive); nasal/facial mask (non-invasive);
- Ventilation mode: volume controlled ventilation (VCV), assist-control (AC) or synchronized intermittent mandatory ventilation (SIMV); pressure controlled ventilation (PCV), AC or SIMV; volume support ventilation (VSV); pressure support ventilation (PSV); synchronized intermittent mandatory ventilation (SIMV) ± pressure support (PS); pressure regulated volume control (PRVC); neurally adjusted ventilatory assist (NAVA); NIV; HFOV; (n)CPAP; BIPAP; and HFNO;
- Ventilator settings: including but not restricted to: expiratory tidal volume (VTe) (mL) or inspiratory tidal volume (VTi) (mL) (only in case VTe is not available); PEEP (cm H2O); PIP (cm H2O) or Pplat (cm H2O) (cm H2O); level of pressure support above PEEP (cm H2O); trigger (flow or pressure, if flow then rate set); FiO2 (%); set and measured RR; I:E ratio; or inspiration time; SpO2 (%); EtCO2 (kPa);
- Arterial blood gas (ABG) analysis results or capillary blood gas (CBG) analysis results, only if available: pH; partial pressure of oxygen (PaO2) (kPa or mmHg); partial pressure of carbon dioxide (PaCO2) (kPa or mmHg);

- Imaging: X-ray (y/n). If yes, the first available X-ray after start of mechanical ventilation, will be assessed by the researcher (to prevent inter-observer variability) whether new opacities (unilateral or bilateral) consistent with acute pulmonary parenchymal disease are seen which are not due primarily to atelectasis or pleural effusion (y/n);

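### Duration of ventilatory support cannot be derived from the listed data for non-invasive-only or stepped-down patients and is ambiguous after reintubation; the ventilation-free-days field does not say which support counts

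*Protocol*

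**What the plan says.** The Summary (Objective) names four outcomes: "duration of ventilatory support, the number of days free from ventilatory support at day 28, length of ICU stay, and ICU mortality". Sections 2.1 and 2.2 repeat them, and the Summary (Main study endpoints) makes the first two secondary endpoints: "Secondary endpoints include the incidence of PARDS, duration of ventilatory support, the number of days free from ventilatory support at day 28". The list in Section 5.1.3 differs. It has "number of ventilation-free days at day 28" and no duration of support.

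Section 4.2 admits any ventilatory support lasting more than 12 hours. Section 4.4 adds that after the first year "we will also start to include patients receiving other types of ventilatory support", among them NIV, CPAP, BiPAP and HFNO.

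On timing, the protocol lists:
- Section 5.2.3: the date of ICU admission, and the date and time of intubation.
- Section 5.2.4: ventilation data, including support type, at the start and then daily "up to day 3, or the day of extubation or death".
- Section 5.2.5, collected at ICU discharge: "Intubated (y/n), and if not, extubation date"; a yes/no item on reintubation within 48 hours, with the reason but no date; and ventilation-free days at day 28, set to zero for death or start of ECMO.

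**The concern.** The outcome is defined on all ventilatory support, but the dates are defined on the tube. For a child who is never intubated, or who leaves the tube for NIV or HFNO, the end of support has no field. After a failed extubation there is one date for two possible events.

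This cannot simply be left to a statistical analysis plan (none was available to this review), because no analysis can recover a date that was never collected. Section 7.1 handles missing data by complete-case analysis, so children without a duration would drop out of that outcome. Section 7.2 plans Kaplan-Meier curves for liberation from the ventilator, which need the same dates. The study runs for 10 years, so the gap grows with each non-invasive cohort.

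Ventilation-free days is a different problem. A number will be entered for each child, but sites in many countries would have to choose for themselves which support counts. That choice could then mix with the geo-economic differences that Section 2.1 sets out to study.

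**Working it through.** The protocol gives no figure for either outcome, so there is none to reproduce. The sample size in Section 4.4 rests on mortality and does not depend on this point. The check matches each outcome to the listed fields.

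**Step 1. Which patients have a start and a stop?**

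| Course | Start listed | Stop listed | Duration of all support |
|---|---|---|---|
| One invasive episode, no later support | Intubation date and time | Extubation date | Derivable, to about a day (no extubation time) |
| Invasive, then NIV/CPAP/BiPAP/HFNO | Intubation date and time | Extubation date only | Not derivable; the later support is left out |
| Reintubated | First intubation | One extubation date, first or last not stated | Ambiguous |
| Non-invasive only | No dedicated field | None | Not derivable |

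**Step 2. How far apart can the readings lie?** The courses below are assumed for illustration; none comes from the protocol. All are survivors without ECMO, with support starting on day 0. Formula: free days = 28 − days counted as support.

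- *Tube to day 5, nothing after.* Duration 5, free days 28 − 5 = 23. Every reading agrees.
- *Tube to day 4, HFNO to day 7.* Tube only: duration 4, free days 28 − 4 = 24. All support: duration 7, free days 28 − 7 = 21. Gap 3 days.
- *Tube to day 5, HFNO to day 12.* Tube only: 5 and 28 − 5 = 23. All support: 12 and 28 − 12 = 16. Gap 7 days.
- *Tube to day 5, reintubated days 8 to 14.* First extubation date: 5 and 23. Last extubation date, read as one interval: 14 and 28 − 14 = 14. Sum of the two episodes: 5 + 6 = 11 and 28 − 11 = 17. The sum needs the reintubation date, which is not listed.
- *NIV only, days 0 to 6.* True values 6 and 28 − 6 = 22. No listed start or stop date yields them.

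**Step 3. Does the ventilation-free-days field close the gap?** It supplies a value for one of the two outcomes, with a rule for death and ECMO. Four things remain open:
- Its name differs from the wording of the objectives, which speak of freedom from ventilatory support.
- It does not say whether non-invasive days count.
- It is completed at ICU discharge, which may come before day 28.
- For the last three rows of the table it cannot be fully checked against listed dates.

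Duration has no directly entered field at all.

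**The case against.** The strongest reply is that the gap is limited. The first-year cohort is invasive only, and a single invasive episode gives a duration from the listed dates. Ventilation-free days is collected directly. Section 5.2.4 starts day 0 at the start of ventilation and records support type to day 3, so the start of non-invasive support is observed indirectly, and a stop within those days might be bracketed. The Summary also keeps data collection minimal on purpose. All of this stands, and it narrows the point. It does not supply a stop date after day 3, support after extubation, or a reintubation date.

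A reader might infer more than the protocol supports in four ways:

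- *That support-free days cannot be obtained at all.* They can be entered directly in Section 5.2.5. The fault is the missing definition.
- *That reintubated children are always scored too favourably.* This holds only if the first extubation date is entered and used. The item asks for status at ICU discharge and can equally be read as the last extubation.
- *That centres which extubate early to NIV or HFNO look better by construction.* This requires the field to ignore non-invasive days, which the protocol does not say. It is a possible consequence.
- *That transfers and long-term ventilated children are further data gaps.* Intubation status, discharge date and destination are recorded, and Section 5.2.2 records the comorbidity ("organ transplant, chronic ventilation"). How to score these children is an analysis rule that can be left to the statistical analysis plan.

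**Conclusion.** The point holds in this limited form. Duration of ventilatory support is a named secondary endpoint. It is not derivable for children on non-invasive support only or for support continued non-invasively after extubation, and it is ambiguous after reintubation. It is also missing from Section 5.1.3. Ventilation-free days will be recorded, but under a definition that leaves open which support counts.

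In the stepped-down examples the two readings differ by 3 and 7 days out of 28; for a single invasive episode they do not differ. These sizes rest on assumed courses. The protocol does not give the share of patients affected, so the effect on any group comparison cannot be stated, and no direction of bias is shown.

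The main endpoint, ICU stay, ICU mortality and the sample size are unaffected. This should be fixed, but it concerns secondary outcomes and does not undermine the study as a whole.

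**What to change.** 1. In Sections 5.2.3 and 5.2.5, add the start date and final stop date of ventilatory support, invasive and non-invasive, up to day 28 or ICU discharge.
2. In Section 5.2.5, add the reintubation date and the final extubation date, and say which extubation the existing item means.
3. Use one definition of support-free days in the Summary and in Sections 2.1, 2.2, 5.1.3 and 5.2.5. State which support types count and how days between ICU discharge and day 28 are filled. If invasive-ventilation-free days are also wanted, name them as a separate endpoint.
4. Add duration of ventilatory support to Section 5.1.3.

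The cost is a few date fields per patient and some wording. That is a small extra load, though a real one given the aim of minimal data collection. The pilot in Section 5.4 is a natural place to test the fields. They should be in place before non-invasive patients are enrolled, and preferably from the start, because step-down and reintubation already occur in an invasive-only cohort.

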#### 7.2. Visualization of endpoints

Data will be visualized using distribution graphs for ventilation settings, variables and parameters, and Kaplan–Meier curves for events like liberation from the ventilator, discharge and death.

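### The definition of successful extubation has no survival condition and no option for an incompletely observed 48-hour window, so some deaths and some late failures are recorded as successes (minor)

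*Protocol*

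**What the plan says.** Protocol section 5.2.5 opens with "Outcome data will be collected at ICU discharge" and then lists the fields. The one at issue is "Successful extubation; defined as no reintubation within 48 hours after extubation (y/n), if not: reason of reintubation". It has one condition and two possible answers.

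Other fields in the same list bear on it:

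- Vital status is a separate item, not linked to the extubation item: "Alive (y/n), and if not, date of death in ICU; cause of death".
- The end of invasive support is recorded as "Intubated (y/n), and if not, extubation date". This is a date without a time.
- Death is handled explicitly in a neighbouring outcome: "Number of ventilation-free days at day 28 (zero in case of death or start ECMO".
- Children may leave to several places: "Destination after ICU discharge (other ICU, ward or home".

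Elsewhere, section 7.2 plans Kaplan-Meier curves for "events like liberation from the ventilator, discharge and death", and section 2.1 aims to "identify potentially modifiable factors that have independent associations with outcome including duration of ventilatory support". Successful extubation itself is absent from the objectives, from the endpoints in the Summary and from the clinical outcomes in section 5.1.3.

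**The concern.** A success measure for extubation should not count a death as a success. As worded, this one does whenever the child dies inside 48 hours without the tube being replaced. Extubation at withdrawal of life-sustaining treatment is the clearest case, because reintubation is then not to be expected. The follow-on request for a reason ties the answer no to reintubation and leaves no place for death.

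The 48-hour window may also run past the point at which the data are collected. If a child leaves the ICU before the window closes, the form still asks for yes or no, and the protocol describes no later contact.

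At stake is the accuracy of any reported extubation success rate. There is also a gap in the collected items: nothing marks an extubation as part of withdrawal of support. The analysis cannot add that marker later if it was never recorded, and the study is planned to run for 10 years.

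**Working it through.** **Step 1. Apply the definition literally.** The protocol states no figure for this item, so the first check is logical.

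| Course after extubation | By the stated definition | As likely recorded at ICU discharge | Sensible reading |
|---|---|---|---|
| Reintubated in the ICU within 48 h | Failure | Failure | Failure |
| Dies within 48 h, not reintubated | Success | Success | Not a success |
| Leaves the ICU within 48 h, never reintubated | Success | Success | Success |
| Leaves the ICU within 48 h, reintubated elsewhere inside the window | Failure | Possibly success | Failure |

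The second row is wrong by the definition itself. The fourth is wrong only through the timing of data collection. The third is correct, so early departure alone is not a misclassification.

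**Step 2. What the other fields can repair.** Extubation and death are both recorded by date. A difference of *d* calendar days (*d* ≥ 1) means an elapsed time between 24(*d* − 1) and 24(*d* + 1) hours:

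- *d* = 0: under 24 h, so inside the window.
- *d* = 1: 0-48 h, so inside the window.
- *d* = 2: 24-72 h, so undetermined.
- *d* = 3: 48-96 h, so outside the window.

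Most ICU deaths can therefore be reclassified afterwards, with ambiguity only at a two-day difference. The same arithmetic on the ICU discharge date flags windows that were not fully observed, but it cannot show whether a reintubation took place elsewhere. No combination of listed fields states directly whether an extubation was for recovery or at withdrawal of support. Cause of death does not record it.

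**Step 3. Bound the size.** Inputs from section 4.4 are 3,300 patients and 3% mortality. Expected deaths are 3,300 × 0.03 = 99, leaving 3,300 − 99 = 3,201 survivors. Suppose all survivors are extubated, and *D* children die within 48 h of extubation without reintubation. If those deaths stay in the denominator, the success rate is inflated by *D* / (3,201 + *D*).

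- Ceiling, all deaths of this kind: 99 / 3,300 = 3.0 percentage points.
- Assumed 30% of deaths: *D* = 30; 30 / 3,231 = 0.9 points.
- Assumed 70% of deaths: *D* = 69; 69 / 3,270 = 2.1 points.

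The 30-70% range is an assumption with no source in the protocol, and it treats every such death as falling within 48 h. The 3% is the protocol's estimate for PICU patients overall. If mortality among ventilated children is higher, the bound rises roughly in proportion. The protocol gives nothing from which to size the fourth row of the table.

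**Step 4. Liberation and duration.** Both would be derived from the extubation date, not from the 48-hour field. A child who dies intubated has no extubation date. A child extubated at withdrawal who dies soon after has one. Without a marker, the second child's extubation cannot be told directly from a recovery extubation.

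**The case against.** The best reply is that little depends on this field. It is a collected item and not a listed endpoint. ICU mortality is an outcome in its own right, and ventilation-free days, the listed outcome that combines survival with ventilation, already score zero for death. Vital status, date of death and extubation date are all recorded, so an analyst can reclassify most early deaths. How death enters the liberation and duration analyses is commonly left to the analysis plan, which is not shown, and section 7.2 already names death as an event of its own. All of this stands, and it is why the point is minor.

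It does not remove the point. The stated rule gives the wrong answer for early deaths, and no other section corrects it. An analysis plan can reclassify by dates, but it cannot supply a withdrawal marker or a reintubation after discharge that the listed fields do not capture.

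A reader might go further and infer that the worst outcome is coded as the best one throughout the extubation, liberation and duration results. The documents do not support that: nothing ties liberation or duration to the 48-hour definition, and rewording it would change neither.

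**Conclusion.** The definition is faulty as written, and the fault is of low severity. Deaths within 48 hours of extubation without reintubation are recorded as successes. Reintubations elsewhere after early ICU departure may be as well. The likely result is a slightly inflated success rate of a size the documents do not allow to be computed. On the planning figures the death part is at most 3.0 percentage points, assuming 3% mortality and all survivors extubated. Separately, extubations at withdrawal of support cannot be identified directly for the liberation curves or for duration of support.

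Two stronger conclusions are tempting and should not be drawn. One is that the misclassification makes harmful settings look neutral or good. That needs children dying after withdrawal to have had the highest pressures and FiO2, which the protocol does not show; withdrawal for non-pulmonary reasons could go with modest settings. The other is that the geo-economic comparison is distorted. That needs withdrawal practice to differ by region, on which the protocol is silent.

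**What to change.** In section 5.2.5:

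1. Define successful extubation as being alive and not reintubated 48 hours after extubation.
2. Code death within 48 hours of extubation as its own category, neither success nor reintubation.
3. Add a not-assessable answer for discharge or transfer before 48 hours, to be used unless the hospital record settles whether reintubation occurred.
4. Add one yes/no item for extubation at withdrawal of life-sustaining treatment, and state that these extubations are not counted as liberation events in the section 7.2 curves.

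The cost is one reworded definition with its answer categories, one extra form item, and a slightly lower reported success rate. Only data collection changes, not care. The pilot in section 5.4, which is meant to find and resolve protocol problems before data collection starts, is a natural place to test the revised form.
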